7.1.1. Does the protocol address confounding by indication if applicable?				
7.2 Does the protocol address: 7.2.1. Selection biases (e.g. healthy user bias)	\boxtimes			10.3.4
7.2.2. Information biases (e.g. misslassification of				10.3.4
7.3 Does the protocol address the validity of the study covariates?			\boxtimes	
Comments:				
Section 8: Effect modification	Yes	No	N/A	Section Number
8.1 Does the protocol address effect modifiers? (e.g. collection of data on known effect modifiers, sub-group analyses, anticipated direction of effect)				
Comments:				
This is a descriptive survey				
Section 9: Data sources	Yes	No	N/A	Section Number
9.1 Does the protocol describe the data source(s) used in the study for the ascertainment of:				
9.1.1 Exposure? (e.g. pharmacy dispensing, general practice prescribing, claims data, self-report, face-to-face interview, etc.)				10.4
9.1.2 Outcomes? (e.g. clinical records, laboratory				10.4
markers or values, claims data, self-report, patient interview including scales and questionnaires, vital statistics, etc.) 9.1.3 Covariates?				

9.2 Does the protocol describe the information

Section 9: Data sources	Yes	No	N/A	Section Number
available from the data source(s) on:				Itallibei
8.2.1 Exposure? (e.g. date of dispensing, drug quantity, dose, number of days of supply				10.4
prescription, daily dosage, prescriber)				10.4
8.2.2 Outcomes? (e.g. date of occurrence, multiple event, severity measures related to event) 8.2.3 Covariates? (e.g. age, sex, clinical and drug use history, co-morbidity, co-medications, life style, etc.)				
9.3 Is a coding system described for:				
9.3.3 Exposure? (e.g. WHO Drug Dictionary, Anatomical Therapeutic Chemical (ATC)Classification System)				
9.3.2 Outcomes? (e.g. International Classification of Diseases (ICD)-10, Medical Dictionary for Regulatory Activities (MedDRA)) 9.3.3 Covariates?				
9.4 Is a linkage method between data sources described? (e.g. based on a unique identifier or other)			\boxtimes	
Comments:				
Section 10: Analysis plan	Yes	No	N/A	Section Number
Section 10: Analysis plan 10.1 Is the choice of statistical techniques described?	Yes	No	N/A	
10.1 Is the choice of statistical techniques		No	N/A	Number
10.1 Is the choice of statistical techniques described?		No	N/A □ □ □	Number 10.7
10.1 Is the choice of statistical techniques described? 10.2 Are descriptive analyses included?		No		Number 10.7
 10.1 Is the choice of statistical techniques described? 10.2 Are descriptive analyses included? 10.3 Are stratified analyses included? 10.4 Does the plan describe methods for adjusting 		No		Number 10.7
 10.1 Is the choice of statistical techniques described? 10.2 Are descriptive analyses included? 10.3 Are stratified analyses included? 10.4 Does the plan describe methods for adjusting for confounding? 10.5 Does the plan describe methods for handling 		No		10.7 10.7.1
 10.1 Is the choice of statistical techniques described? 10.2 Are descriptive analyses included? 10.3 Are stratified analyses included? 10.4 Does the plan describe methods for adjusting for confounding? 10.5 Does the plan describe methods for handling missing data? 10.6 Is sample size and/or statistical power 		No		10.7 10.7.1
 10.1 Is the choice of statistical techniques described? 10.2 Are descriptive analyses included? 10.3 Are stratified analyses included? 10.4 Does the plan describe methods for adjusting for confounding? 10.5 Does the plan describe methods for handling missing data? 10.6 Is sample size and/or statistical power estimated? 		No		10.7 10.7.1
 10.1 Is the choice of statistical techniques described? 10.2 Are descriptive analyses included? 10.3 Are stratified analyses included? 10.4 Does the plan describe methods for adjusting for confounding? 10.5 Does the plan describe methods for handling missing data? 10.6 Is sample size and/or statistical power estimated? 		No		10.7 10.7.1

Section 11: Data management and quality control	Yes	No	N/A	Section Number			
archiving)							
11.2 Are methods of quality assurance described?	\boxtimes			10.8			
11.3 Is there a system in place for independent review of study results?				10.6.1			
Comments:							
Section 12: Limitations	Yes	No	N/A	Section Number			
12.1 Does the protocol discuss the impact on the study results of:							
12.1.1 Selection bias?				10.9			
12.1.2 Information bias?	\boxtimes			10.9			
12.1.3 Residual/unmeasured confounding?	\boxtimes			10.9			
(e.g. anticipated direction and magnitude of such biases, validation sub-study, use of validation and external data, analytical methods)							
12.2 Does the protocol discuss study feasibility? (e.g. study size, anticipated exposure, duration of follow-up in a cohort study, patient recruitment)				10.10			
Comments:							
Section 13: Ethical issues	Yes	No	N/A	Section			
			,	Number			
13.1 Have requirements of Ethics Committee/ Institutional Review Board been described?				11			
13.2 Has any outcome of an ethical review procedure been addressed?				11			
13.3 Have data protection requirements been described?				11			
Comments:							
Section 14: Amendments and deviations	Yes	No	N/A	Section Number			
14.1 Does the protocol include a section to document amendments and deviations?	\boxtimes			6			
Comments:							

Section 15: Plans for communication of study results	Yes	No	N/A	Section Number
15.1 Are plans described for communicating study results (e.g. to regulatory authorities)?				13
15.2 Are plans described for disseminating study results externally, including publication?				13
Comments:				
Name of the main author of the protocol: PPD				
Date: / / Signature:				

WWEpi Project number: PRJ2678/205881

16. ANNEX 4: HEALTHCARE PROVIDER SURVEY

The purpose of this survey is to assess your understanding of the risks associated with Strimvelis gene therapy.

SCREENING QUESTIONS	Yes	No	I don't know
Are you or any of your close family members an employee of GlaxoSmithKline, Pharmaceutical Product Development, LLC (PPD), the Food and Drug Administration (FDA), or the European Medicines Agency (EMA)?	[Terminate]		[Terminate]
This survey is voluntary. Do you agree to take part in this survey?		[Terminate]	[Terminate]
We appreciate your participation, no payment for completion of the survey can be provided. Do you wish to continue with the survey?		[Terminate]	[Terminate]
Have you previously taken part in a survey of your knowledge of educational materials about Strimvelis?	[Terminate]		
Are you a licensed medical healthcare provider?		[Terminate]	[Terminate]
Have you previously referred one of your patients to an Italian Strimvelis treatment centre?		[Terminate]	[Terminate]

DEMOGRAPHY QUESTIONS:

-
Demography Q1: How many patients have you referred to for treatment with Strimvelis?
Demography Q2: How would you classify your primary medical speciality?
Please select one response.
a. Paediatrician
b. Immunologist
c. Haematologist
d. Other (please specify):
Demography Q3: In what country is your primary medical practice?
Demography Q4: What is the length of your experience in your primary medical speciality?

WWEpi Project number: PRJ2678/205881

- a. Less than 3 years
- b. More than 3 and up to 5 years
- c. More than 5 and up to 10 years
- d. More than 10 and up to 15 years
- e. More than 15 years
- f. Prefer not to answer

Demography Q5: How many patients with ADA-SCID are you currently treating?

<#>

MAIN SURVEY QUESTIONS:

1. Have you received copies of the following educational materials about Strimvelis for healthcare providers?

Select all that apply.

- a. Important risk minimization information for healthcare professionals who provide long-term follow-up of ADA-SCID patients post-treatment with Strimvelis.
- b. Summary of Product Characteristics (SmPC).

If you answered "No" to all of the above materials, prior to this survey, were you aware of these educational materials about Strimvelis?

Please select one response.

- a. Yes
- b. No
- c. I don't know (I cannot remember)
- 2. Did you read the provided educational materials about Strimvelis?

Please select one response.

a. Yes
b. No
c. Some
d. I don't know
If Some, which ones did you read?
Please answer based on your knowledge of Strimvelis as informed by the Strimvelis Educational Materials, including the product Summary of Product Characteristics (Product Label).
3. Strimvelis is recommended as first-line therapy for any patient affected by ADA-SCID.
Please select one response.
a. True
b. False
c. I don't know
4. Strimvelis is indicated for the treatment of patients with severe combined immunodeficiency due to ADA deficiency, for whom no suitable HLA matched related stem cell donor is available.
Please select one response.
a. True
b. False
c. I don't know
5. Strimvelis is contraindicated in patients with a history of previous gene therapy.
Please select one response.
a. True
b. False

c. I don't know

CONFIDENTIAL

WWEpi Project number: PRJ2678/205881

6. Patients eligible to receive treatment with Strimvelis should have a bone marrow harvest for stem cell back-up at least 3 weeks prior to treatment with Strimvelis. Please select one response. a. True b. False c. I don't know 7. Parents and carers of patients receiving treatment with Strimvelis should be educated on the fact that the patient should not be able to donate blood, organs, tissues, or cells for transplantation. Please select one response. a. True b. False c. I don't know 8. It is recommended that patients treated with Strimvelis are regularly followed up clinically (at least annually). Please select one response. a. True b. False c. I don't know 9. Strimvelis is contraindicated in patients with a current or previous history of leukaemia or myelodysplasia. [KRM 1] Please select one response. a. True b. False

c. I don't know

CONFIDENTIAL

WWEpi Project number: PRJ2678/205881

10. Have you given advice to parents/carers/patients regarding monitoring for signs and symptoms of leukaemia? [KRM1] Please select one response. a. Yes b. No c. I don't know 11. Have you performed blood tests (including red blood cell indices, white blood cell count differential, platelet count, and a routine biochemistry screen) within the first year of a patient's returning from treatment with Strimvelis? [KRM1] Please select one response. a. Yes b. No c. I don't know 12. Regular monitoring for clinical autoimmunity (possibly including tests for auto-antibodies) is recommended. [KRM2] Please select one response. a. True b. False c. I don't know 13. Autoimmunity may be observed during immune reconstitution after gene therapy. [KRM2] Please select one response. a. True b. False

b. No

c. I don't know

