8.3. Survey design

8.3.1. Survey Instruments

There are two survey instruments included in this study, (1) a HCP survey and (2) a parent/carer survey.

Following agreement to participate, the understanding of the potential risks associated with Strimvelis will be evaluated via telephone interview. The telephone interviews will be conducted in the local countries language. The survey will start with screening questions to ensure eligibility and willingness to participate in the survey. Participation in the study can be terminated during screening. The survey will include multiple choice and close-ended questions. There will be no open-ended questions included.

Survey questions are based on the Strimvelis prescribing information and educational materials including those that address risks of autoimmunity, unsuccessful response, oncogenesis and pregnancy. There will be approximately 20 questions per survey.

For HCPs, the survey refers to the following risk minimisation measures:

- Educational materials:
 - Important risk minimisation information for healthcare professionals who provide long-term follow-up of ADA-SCID patients post-treatment with Strimvelis
- Strimvelis Summary of Product Characteristics

For parents/carers, the survey refers to the following risk minimisation measures:

- Educational materials:
 - "Important follow-up risk minimisation information for children who have received gene therapy with Strimvelis (autologous CD34+ cells transduced to express ADA) an educational leaflet for parents/carers"
 - Patient Treatment Alert Card
- Strimvelis Patient Information Leaflet

The questions will evaluate HCPs' and patients'/carers' understanding of the key risk messages (KRMs) of the routine and additional risk minimisation measures. The questions will also assess HCPs' and patients'/carers' awareness, receipt, and reading of the educational materials. Demographic information such as geographic region and HCP specialty will also be captured (see Annexes 4 and 5). This information is required to further characterise the respondent population, including the number of patients.

The KRM topics for both the HCP and parent/carer surveys are listed in Section 8.3.3:

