8.3.4. Measures to Minimise Bias in the Surveys

The following are measures to minimise bias in the surveys:

All questions will be programmed to ensure that questions are asked in the appropriate sequence. Skip patterns will be clearly indicated. Respondents cannot go back to a

question once the question has been answered and cannot skip ahead. All questions must be answered in order to complete the survey. This is important because subsequent questions could provide answers to previous questions, and because all subjects should have the same chance of answering the questions correctly. Other biases are described in the limitation section, however, cannot be minimized by survey design alone.

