14. ANNEX 2: LIST OF TABLE AND FIGURE SHELLS

14.1. Tables

Table 1. Survey participant summary

	HCP survey	Parent/Carer survey	
Number of participants screened			
Number of participants terminated			
Number of participants completed the survey			
Total			

 Table 2: HCP survey - availability and review of Educational Materials

	Yes (N, %)	No (N, %)	Total (N, 100%)	
 Have you received copies of the following Educational Materials on Strimvelis for healthcare practitioners? Important risk minimization information for healthcare professionals who provide long- term follow-up of ADA-SCID patients post- treatment with Stimvelis. Summary of Product Characteristics (SmPC). 				
If you answered "No" to all of the above materials, prior to this survey, were you aware of these educational materials about Strimvelis?				
	Yes	No	Some	N total (% Yes)
Did you read the provided Educational Materials about Strimvelis?				
 If Some, which ones did you read? Important risk minimization information for healthcare professionals who provide long-term follow-up of ADA-SCID patients post-treatment with Strimvelis. Summary of Product Characteristics (SPC). 				

Table 3. Listing of HCP Survey Responses for each survey question

Survey Question	Answer	N	% (total)
Demography Q1. How			
many patients have you			
referred to for treatment			

Survey Question	Answer	N	% (total)
with Strimvelis?			
Demography Q2. How would you classify your	a. Paediatrician		
<pre>primary medical speciality?</pre>	b. Immunologist		
	c. Haematologist		
	d. Other (please specify):		
Demography Q3. In what country is your primary medical practice?			
Demography Q4. What is the length of your	a. Less than 3 years		
experience in your primary medical speciality?	b. More than 3 and up to 5 years		
	c. More than 5 and up to 10 years		
	d. More than 10 and up to 15 years		
	e. More than 15 years		
	f. Prefer not to answer		
Demography Q5. How many patients with ADA-SCID are you currently treating?			
1. Have you received copies of the following educational materials about Strimvelis for healthcare providers?	a. Important risk minimization information for healthcare professionals who provide long-term follow-up of ADA-SCID patients post-treatment with Strimvelis.		
	b. Summary of Product Characteristics (SPC).		

Survey Question	Answer	N	% (total)
If you answered "No" to all of the above	a. Yes		
materials, prior to this survey, were you aware	b. No		

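### HCP Q2 asks once about reading 'the provided' materials, with no receipt skip and no split of 'Yes' by material, so the Table 2 '% Yes' does not show who read the leaflet

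*Protocol*

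**What the plan says.** Section 8.3.1 of the Protocol gives the purpose: "The questions will also assess HCPs' and patients'/carers' awareness, receipt, and reading of the educational materials". For HCPs it lists the leaflet under educational materials and gives "Strimvelis Summary of Product Characteristics" as a separate entry. Sections 6.2 and 7 distinguish routine measures (labelling) from additional ones (educational materials).

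In Annex 4, Q1 records receipt of each document but places the SmPC among the educational materials. An HCP who received neither is routed to an awareness question. Q2 follows as a single item, "Did you read the provided educational materials about Strimvelis", with the options Yes, No, Some and I don't know. The only follow-up by material is "If Some, which ones did you read".

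Table 2 (Annex 2, section 14.1) repeats the item as "Did you read the provided Educational Materials about Strimvelis" with columns for Yes, No and Some, then N total with the percentage of Yes. 'Some' is itemised by document. Table 3 lists all four Q2 options.

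Section 8.3.4 promises "Skip patterns will be clearly indicated" and requires every question to be answered before a survey is complete. Section 8.7 analyses all respondents.

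**The concern.** Reading is meant to show whether delivered materials were used. To do that, the figure must say which document was read and must be taken over people who had it. The Table 2 percentage does neither reliably.

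A high value may come partly from the SmPC, which is a routine measure, and say little about the leaflet, which is the additional measure. A low value may mean that the material never arrived, or that it arrived and was not read. Failed distribution and unread material call for different responses from the sponsor.

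**Working it through.** The Protocol gives no figure for reading, so there is none to reproduce. The check follows each type of HCP through Q1, Q2 and Table 2, then counts at the planned 10 HCPs (section 8.5).

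**Tracing the answers**
- Received both, read both: 'Yes'. Counted correctly.
- Received both, read only the SmPC: 'Some', then itemised. Outside '% Yes' and counted correctly.
- Received and read only the SmPC: 'Yes' is truthful, because that is all that was provided. In the reading row this HCP looks like a leaflet reader.
- Received nothing: no option fits, no skip is marked, and an answer is required. 'No' merges this HCP with recipients who did not read. 'I don't know' has no Table 2 column.

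**Counts.** Let a = received and read both, b = received both and read only the SmPC, c = received and read only the SmPC, d = received nothing. Take N total as all 10.
- '% Yes' = (a + c)/10
- Leaflet read, all respondents = a/10
- Leaflet read, its recipients = a/(a + b)

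The splits below are assumptions for illustration.

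| a | b | c | d | % Yes | Leaflet, of all 10 | Leaflet, of its recipients |
|---|---|---|---|---|---|---|
| 8 | 0 | 0 | 2 | 8/10 = 80% | 8/10 = 80% | 8/8 = 100% |
| 6 | 0 | 2 | 2 | 8/10 = 80% | 6/10 = 60% | 6/6 = 100% |
| 3 | 0 | 5 | 2 | 8/10 = 80% | 3/10 = 30% | 3/3 = 100% |
| 5 | 5 | 0 | 0 | 5/10 = 50% | 5/10 = 50% | 5/10 = 50% |

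The first three rows share a '% Yes' of 80%, while leaflet reading over all respondents runs from 30% to 80%. The last row shows 'Some' working as intended.

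**Size per respondent**
- Each HCP in group c adds 1/10, or 10 points, to '% Yes' over a/10.
- For non-recipients, let y be the number answering 'Yes' and r = 10 − d the number who received anything. The gap is y/r − y/10 = (y/r) × d/10, so each non-recipient costs 10 × (y/r) points, at most 10.
- If 'I don't know' is dropped from N total and both non-recipients in the second row gave that answer, the row would read 8/8 = 100% instead of 80%.

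**Do the Table 2 margins settle it?** Not always. Suppose 6 HCPs received both documents, 2 the SmPC only and 2 nothing.
- Pattern A: all 6 with both say 'Yes'; the 2 SmPC-only and the 2 non-recipients say 'No'.
- Pattern B: 4 of the 6 say 'Yes' and 2 'No'; the 2 SmPC-only say 'Yes'; the 2 non-recipients say 'No'.

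Both give leaflet received 6, SmPC received 8, awareness row 2, and reading Yes 6, No 4, Some 0. Leaflet reading among its recipients is 6/6 = 100% in A and 4/6 = 67% in B.

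**The case against.** The instrument itself counts the SmPC as an educational material, so 'Yes' from an SmPC-only recipient is a correct answer to the question put. That stands, but section 8.3.1 lists the two separately, and the percentage cannot be read as leaflet reading.

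Table 2 shows receipt per document beside reading, and an awareness row counts those who received nothing. In simple patterns this is enough. With 6 HCPs who received and read both and 4 who received nothing, the shortfall is visibly one of distribution. Patterns A and B show that it is not enough in general.

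Q1 and Q2 are both collected, so a cross-tabulation could recover most of the information, and section 8.6.2 leaves a reporting analysis plan to the CRO. That limits the harm. The question wording and table shells are nevertheless fixed in this Protocol, and no shell plans the cross-tabulation.

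The programmed survey may contain a skip that is not printed. Annex 4 prints its other routing, however, and shows none at Q2.

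A reader might infer that every HCP who read only the SmPC is counted as having read the leaflet. The documents do not support this: an HCP who received both goes to 'Some'. Nor are 'I don't know' answers lost altogether, since Table 3 lists them.

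**Conclusion.** The point holds as a minor one. The Table 2 '% Yes' measures neither reading of the leaflet nor reading among recipients. At 10 HCPs the distortion is 10 points upward for each SmPC-only recipient who read it, measured against all respondents. It is up to 10 points downward for each non-recipient, measured against recipients. This assumes that HCPs answer literally, that no unprinted skip exists, and that N total is all respondents.

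A reader might infer one fixed error, such as 40 points. The documents give no split from which to derive it, and the figure depends on the comparator. With 5 HCPs who received and read both, 4 who received and read only the SmPC and 1 who received nothing, '% Yes' is 90%. The gap is 40 points against all respondents (50%) and 10 against leaflet recipients (100%). With 6 who received and read both and 4 who received nothing, '% Yes' is 60%, and the gaps are 0 and 40.

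A reader might also infer that the main result is affected. Section 8.3.3 makes correct responses the primary outcome and applies the 80% criterion to key risk messages, and Q2 belongs to none of them. Table 4 does carry Q2 into its Q1-5 and Q1-20 totals, but the Protocol does not say what a correct answer to Q2 would be, so no effect there can be sized.

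**What to change.** In Annex 4, ask Q2 separately for each document reported as received in Q1, and mark a skip for any document not received. In Table 2, report reading of each document over its recipients and over all respondents, and add an 'I don't know' column. If the question cannot be changed, add a Q1-by-Q2 cross-tabulation as the minimum.

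For parents/carers, add the receipt skip, the recipients' denominator and the 'I don't know' column to Table 6; Table 7 already allows that answer. Their item asks about 'these' rather than 'the provided' materials, so a 'Yes' from someone given only one document is less likely.

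The cost is one or two extra short items and their re-translation, or one extra table. The wording is best settled before interviews start, because section 8.2 excludes anyone who has already completed a survey on the Strimvelis educational materials.

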7. RESEARCH QUESTION AND OBJECTIVE(S)

The objective of this study is to evaluate the effectiveness of routine and additional risk minimization measures (*e.g.* SmPC/PIL, educational materials) by assessing the understanding of parents/carers and referring HCPs with regard to the following:

Safety concerns:

- Malignancy due to insertional oncogenesis (e.g. leukaemia, myelodysplasia)
- Autoimmunity
- Unsuccessful response to gene therapy
- Pregnancy

Other areas of interest:

- Requirement for long-term monitoring
- Patient alert card

This study will help determine whether the current routine and additional risk minimisation measures have been successfully implemented. The study will assess the proportion of parents/carers and referring HCPs providing correct responses to a series of questions concerning specific risks associated with Strimvelis. Additional analyses will assess implementation metrics (e.g. proportion of respondents who received the educational materials).

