8.3.3. Outcome definitions

This study will assess the proportion of parents/carers and referring HCPs at six months post treatment with Strimvelis that understood the possible risks relating to:

Safety concerns (KRM topics):

- 1. Malignancy due to insertional oncogenesis (e.g. leukaemia, myelodysplasia)
- 2. Autoimmunity
- 3. Unsuccessful response to gene therapy
- 4. Pregnancy

Other areas of interest:

- Requirement for long-term monitoring
- Receipt of the patient treatment alert card

The proportion of parents/carers and referring HCPs who acknowledge receipt of routine and additional risk minimization measures (e.g., SmPC/PIL, educational materials, Patient Alert Card) will be assessed as a measure of implementation.

The type of medical specialty and experience of referring HCPs will be summarized.

The primary outcome of these surveys is the proportion of parents/caregivers and referring HCPs that provide correct responses to a series of questions concerning the specific risks associated with Strimvelis.

Sufficient understanding of a key risk message can be assumed if at least 80% or more respondents correctly answer all questions that are included within that particular key risk message [ISPE White Paper 2016].

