8.5. Study size

All parents/carers and referring HCPs from patients enrolled in the Strimvelis product registry will be invited to complete the surveys. The study will recruit for approximately two years until 10 referring HCPs and 10 parents/carers have completed their respective surveys (length of study may vary contingent upon product uptake).

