5. You should report any concerning signs or	a. True		
symptoms that you	b. False		

Survey Question	Answer	N	%
notice after your child is treated with Strimvelis to your child's specialist doctor.	c. I don't know		
KRM 1: Gene therapy f	or ADA-SCID and risk of	of blood cancer (e.g. leu	ikaemia)
6. Your child's specialist doctor will	a. True		
check your child's blood for any signs of	b. False		
leukaemia during check-ups.	c. I don't know		
7. Within the last last 6 months, has your child	a. Yes		
been seen by their specialist doctor for	b. No		
follow-up after receiving Strimvelis?	c. I don't know		
If you answered "Yes," approximately how many times have you seen your child's specialist doctor?			
If you answered "Yes,"has your child	a. Yes		
given blood samples at least once within the	b. No		
last 6 months?	c. I don't know		
8. How often should your child be followed	a. At least once a year		
up by his or her specialist doctor?	b. Every 5 years		
	c. Every 10 years		
KRM 2: Autoimmunity			
9. Autoimmunity occurs when the body's	a. True		
immune system sees its own tissues and cells as	b. False		
foreign and attacks these healthy cells.	c. I don't know		
Symptoms may include a high temperature,			

Survey Question	Answer	N	0/0
rash, joint pain, painful or weak muscles, or feeling tired or unwell most of the time. If you are concerned about autoimmunity, you should contact your specialist doctor.			
10. Autoimmunity can occur (select all that apply):	a. Before treatment because of the disease b. After treatment as the immune system is restored		
	c. Both		
KRM 3: Unsuccessful re	esponse to gene therapy		,
11. Gene therapy is designed to treat the	a. True		
immune issues of ADA-SCID, including	b. False		
frequent severe infections.	c. I don't know		
12. Gene therapy is designed to treat non-	a. True		
immune issues such as fatty liver, reduced	b. False		
hearing, or behavioural problems.	c. I don't know		
13. Immune and non- immune issues will be	a. True		
followed up during routine visits by your	b. False		
child's specialist doctor.	c. I don't know		
14. Symptoms such as fever, cough, loose	a. True		
stools, pain on passing urine may suggest	b. False		
infection and should be reported to your specialist doctor	c. I don't know		

Survey Question	Answer	N	0/0
KRM 4: Pregnancy			
15. Strimvelis is not designed to correct the	a. True		
genetic defect in your child's reproductive	b. False		
cells.	c. I don't know		

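### In three of the eight survey-by-risk-message sets, no item asks directly about the named risk, so a pass under the 80% rule need not mean that the risk is understood

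*Protocol*

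**What the plan says.** Protocol section 7 lists four safety concerns whose understanding is to be assessed, the first being "Malignancy due to insertional oncogenesis (e.g. leukaemia, myelodysplasia". Section 8.3.3 repeats the list, with "Unsuccessful response to gene therapy" as the third topic, and describes the outcome as the proportion of respondents "that understood the possible risks relating to" those topics. It then sets the rule for each topic: "Sufficient understanding of a key risk message can be assumed if at least 80% or more respondents correctly answer all questions" in that message. Under section 8.5, recruitment runs until "10 referring HCPs and 10 parents/carers have completed their respective surveys".

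The items appear in Annex 4 (HCP survey) and in the Annex 2 table shells. HCP KRM1 is Q9 to Q11 in Table 3 and Annex 4, where Q9 reads "Strimvelis is contraindicated in patients with a current or previous history of leukaemia or myelodysplasia. [KRM 1"; Table 4 groups Q6 to Q11 under malignancy. Parent KRM1 is Q6 to Q8 and parent KRM3 is Q11 to Q14 (Tables 7 and 8).

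**The concern.** The outcome is understanding of a risk, so each set should hold at least one item that a respondent unaware of that risk would tend to get wrong. In the three sets at issue, the items concern patient selection, care already given, monitoring, treatment scope and symptom reporting. These follow from the risk or accompany it, but none puts the risk to the respondent.

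The label on the result is what is at stake. A pass on HCP or parent KRM1 would be reported as understanding of insertional oncogenesis, and a pass on parent KRM3 as understanding that treatment may not work. The results go to the EMA as evidence on risk minimisation (sections 11.1 and 11.2). Analysis cannot repair the gap later: the survey is administered once with no follow-up (8.6.3), and anyone who has completed one is no longer eligible (8.2).

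**Working it through.** The protocol gives no power or precision figure to reproduce. The check is a comparison of item content with the outcome, followed by an illustration.

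**Item content**

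| Set | Item content | Direct items on the risk |
|---|---|---|
| HCP KRM1, malignancy (Q9–11) | Q9 contraindication; Q10 advice given on monitoring for leukaemia; Q11 blood tests done | 0 of 3 |
| Same, Table 4 grouping (Q6–11) | adds Q6 stem cell back-up, Q7 donation, Q8 annual follow-up | 0 of 6 |
| Parent KRM1, malignancy (Q6–8) | Q6 doctor will look for signs of "leukaemia during check-ups"; Q7 child seen in the last 6 months; Q8 how often follow-up is due | 0 of 3 |
| Parent KRM3, unsuccessful response (Q11–14) | Q11–12 what the therapy is designed to treat; Q13 follow-up of issues; Q14 reporting infection symptoms | 0 of 4 |

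The same surveys do ask directly elsewhere. HCP Q13 and parent Q10 ask whether autoimmunity can occur after treatment. HCP Q17 and Q18 ask about failure or loss of efficacy. A direct item is therefore feasible in this format.

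**Illustration of the 80% rule**

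With 10 respondents per survey, the rule needs 0.8 × 10 = 8 with all items correct. Let q be the chance that a respondent unaware of the risk answers one item correctly, and k the number of items. The protocol does not give q, so it is an assumption shown over a range. Treating items as independent, P(all correct) = q^k. If all 10 respondents are unaware, the chance of a pass is P(X ≥ 8) with X ~ Binomial(10, q^k).

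| q | k = 3: q^k → P(pass) | k = 4: q^k → P(pass) | k = 6: q^k → P(pass) |
|---|---|---|---|
| 1/3 | 0.037 → 0.000 | 0.012 → 0.000 | 0.001 → 0.000 |
| 0.80 | 0.512 → 0.064 | 0.410 → 0.014 | 0.262 → 0.001 |
| 0.90 | 0.729 → 0.464 | 0.656 → 0.275 | 0.531 → 0.081 |
| 0.95 | 0.857 → 0.839 | 0.815 → 0.721 | 0.735 → 0.481 |
| 1.00 | 1.000 → 1.000 | 1.000 → 1.000 | 1.000 → 1.000 |

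Blind guessing among three options (q = 1/3) almost never passes. The weakness matters only if the items can be answered from ordinary follow-up habits or from their own wording.

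**Effect of one direct item**

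Let g be the assumed chance that an unaware respondent gets the added item right, so that P(all correct) = q^k × g.

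| q | g | P(pass), original k = 3 | P(pass), original k = 4 |
|---|---|---|---|
| 0.95 | 0 | 0.0000 | 0.0000 |
| 0.95 | 1/3 | 0.0011 | 0.0008 |
| 0.95 | 1/2 | 0.0198 | 0.0139 |
| 1.00 | 1/3 | 0.0034 | 0.0034 |
| 1.00 | 1/2 | 0.0547 | 0.0547 |

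**The case against.** **The items are proxies.** HCP Q9 and Q10 and parent Q6 name leukaemia, and an HCP who sees no leukaemia risk is less likely to have given the advice in Q10. In parent KRM3, Q11 with Q14 touches on loss of benefit through infection. This stands in part: the risk is approached indirectly, and it would be wrong to say that respondents are asked nothing connected with it. But Q10 and Q11 record behaviour, Q11 lists routine tests, Q7 records attendance, and parent Q6 supplies the link to leukaemia in its own stem.

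**The items may match the materials.** Section 8.3.1 says the questions are based on the prescribing information and educational materials, whose titles concern follow-up. Those texts are not at hand, so their emphasis cannot be judged. The outcome in 8.3.3 is nevertheless understanding of the possible risks, and section 6.2 says the materials address these concerns specifically.

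**Parent Q4 covers it.** Q4 asks whether there are no risks at all. It names neither malignancy nor failure and sits outside every KRM.

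**The study is descriptive.** Results are reported for every question (8.7.1), so a careful reader can see what was asked, and no inferential test depends on the KRM label. This stands and lowers the severity. The review of questions in section 8.8 is for readability and understanding; it does not check whether the items cover the risk.

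**Stronger readings that the documents do not support.** A reader might infer that the study's objective as a whole goes unmeasured. Five of the eight sets are unaffected, as are the aims on monitoring, the alert card and receipt of materials. A reader might also add the sets together and say that one unaware person could answer all ten items correctly. No one is asked ten: three belong to the HCP survey and seven to the parent survey, and the two are distinct and unlinked (8.2).

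**Conclusion.** The point holds for three sets: HCP KRM1, parent KRM1 and parent KRM3. None has a direct item on its named risk, whichever HCP grouping is used. The 8.3.3 rule would therefore let understanding be assumed for one of four concerns in HCPs (malignancy) and two of four in parents (malignancy and unsuccessful response) without that risk having been asked about directly. HCP KRM3 does ask about failure and is not affected.

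How often unaware respondents would pass is unknown. The illustrative probabilities run from about 0 to 1.00 depending on q, and they rest on independent items and on all ten respondents being unaware. They show that a misleading pass is possible, not that it is likely.

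Parent items and HCP Q14 to Q20 were read from the Annex 2 shells, because the parent survey annex is not in the text at hand and Annex 4 breaks off after Q13. The point should be fixed before data collection, but it does not undermine the whole study.

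**What to change.** Before data collection, add or substitute one True / False / I don't know item in each of the three sets:

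- **HCP KRM1 and parent KRM1:** whether leukaemia or another blood cancer is a possible risk of the gene therapy.
- **Parent KRM3:** whether the gene therapy may not work or may lose its effect.

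Take the wording from the approved SmPC/PIL and the educational leaflets. Place each item before the monitoring items in its set (in HCP KRM1, ahead of Q9), since section 8.3.4 itself notes that later questions can give away earlier answers. Include each in the all-correct rule of 8.3.3. Vary whether True or False is the correct answer, so that a tendency to agree does not inflate the pass rate.

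If the surveys cannot change, label these three outcomes as knowledge of monitoring, indication and reporting, and do not claim understanding of malignancy or unsuccessful response from them.

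If the items are added, the parent survey grows from 16 to 18 and the HCP survey from 20 to 21 (or stays at 20 by substitution), against the roughly 20 per survey in section 8.3.1. The cost is a slightly longer interview, extra translation and probably lower pass rates.
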